# 8.6 DATA EXTRACTION

Data for the pre-surgery and surgery visits will be collected retrospectively onto CRFs. The data collected will be in accordance with Table 1 (8.1: Study Schedule).

Following signing of consent form, a subject ID number will be assigned consisting of a two-digit study identification number, a two-digit site identification number followed by a two-digit subject number (e.g., 16-02-01). Subject ID numbers will be assigned sequentially.

Medical records will be reviewed for demographic and medical history information, preoperative, medication use data, and adverse events. Surgical information including clock hours of canaloplasty and trabeculotomy, intra-operative complications will be abstracted from the Operative Notes.

## 8.7 PROSPECTIVE VISITS

After obtaining an understanding of the purpose of this study, then reviewing and signing the Informed Consent Document, all subjects will begin the prospective study visits. These visits should be performed according to the schedule provided in Tables 1 and 2. All attempts should be made to conduct each visit within the time interval specified in Tables 1 and 2. Evaluations conducted outside the prescribed time period will be considered protocol deviations.

NOTE: A safety IOP check anytime between the predefined visits may be performed at the Investigator's discretion whenever warranted to ensure subject safety and should be documented as unscheduled visit.

## 8.7.1 WASHOUT OF HYPOTENSIVE MEDICATIONS

Subjects that had undergone a preoperative medication washout and who are on ocular hypotensive medication at the 12- and 24-month pos-operative visits will be instructed to discontinue their ocular hypotensive medication regimen, and to return for a post-washout visit after completing the appropriate washout period.

Glaucoma medication discontinuation can be staged so that the pressure increase duration is minimized to the greatest possible extent during the washout period. For example, if a patient is on a prostaglandin (PGA) and a Carbonic Anhydrase Inhibitor (CAI), the PGA could be discontinued 4 weeks prior to the Baseline measurement but the CAI allowed to continue until 5 days before Baseline.

If the study subject fails to remember to not use ocular hypotensive medication for the study eye per the required washout period, they can restart washout and return for the appropriate visit upon completion of washout and as long as it falls within the specified visit window. The minimum wash-out periods are specified in Table 2 below.

Brand Name/Chemical Name	Minimum washout period
Carbonic Anhydrase Inhibitors	
Diamox ® (Acetazolamide) – oral Rx	5 days
Neptazane ® (Methazolamide) – oral Rx	5 days
Azopt ® (Brinzolamide)	5 days
Trusopt ® (Dorzolamide Hydrochloride)	5 days
Muscarinic Agonists	
Salagen, Pilocar (Pilocarpine)	5 days
Alpha Adrenergic Agonists	
Alphagan ® (Brimonidine)	14 days
lopidine ® (Apraclonidine Hydrochloride)	14 days
Beta Blockers	
Betagan ® (Levobunolol Hydrochloride)	28 days
Betoptic ® (Betaxalol Hydrochloride)	28 days
OptiPranolol ® (Metipranolol)	28 days
Timoptic/Betimol ® (Timolol Maleate)	28 days
Prostaglandin Analogs	
Lumigan ® (Bimatoprost)	28 days
Travatan ® (Travoprost)	28 days
Xalatan ° (Latanoprost)	28 days
Zioptan ® (Tafluprost)	28 days
Vyzulta® (Latanoprostene Bunod)	28 days
Rho Kinase Inhibitor	
Rhopressa ® (Netarsudil)	28 days
Fixed Combination Medications	
Combigan ® (Brimonidine Tartrate/Timolol Maleate)	28 days
Cosopt ® (Dorzolamide Hydrochloride/ Timolol	28 days
Maleate)	
DuoTrav® (Travoprost/Timolol)	28 days
Ganfort® (Bimatoprost/Timolol)	28 days

#### **Table 3: Ocular Hypotensive Medication Washout Periods**

CONFIDENTIAL

Rev C

Rocklatan ® (Netarsudil/Latanoprost)	28 days
Simbrinza ® (Brinzolamide/Brimonidine Tartrate)	28 days
Xalacom ® (Latanoprost/Timolol) 28 days	
Krytantek (Brimonidine Tartrate/ Dorzolamide	28 days
Hydrochloride/ Timolol Maleate)	
Other	Contact Sponsor

NOTE: A safety IOP check anytime during the wash-out period may be performed at the Investigator's discretion to ensure subject safety and should reported as unscheduled visits.

#### 8.8 **UNSCHEDULED VISITS**

An unscheduled visit will be any visit to the clinical site, other than those specified in the protocol, at which the subject has a complaint regarding the study eye and/or treatment to the study eye is required or changed. The Investigator and/or qualified investigational staff will perform the procedures necessary to evaluate the study participant at these visits and will record the visit in the subject's medical records and on the CRF. No specific testing is required.

#### 8.9 **MANAGEMENT OF IOP**

For subject safety, a change in medical therapy may be implemented or additional surgical measures may be performed at any time during the study at the Investigator's discretion in the event it is required. The primary concern of the Investigator and Sponsor at all times is the health and safety of the subjects. Usage of hypotensive medications specifically indicated for prevention of IOP spikes following Nd:YAG capsulotomy and administered for up to 72 hours after Nd:YAG capsulotomy will not be considered rescue therapy.

Medications which have been re-started by the Investigator may be discontinued if the Investigator's judgment is that the target intraocular pressure has been reached and the continued use of some or all of the therapy may not be required. Discontinuation of medications after re-introduction is recommended to be in the reverse order of reintroduction. The rationale for discontinuation should also be documented in the subject's medical record.

A record of all ocular hypotensive medications added, discontinued or changed will be documented on the appropriate CRF for each scheduled visit or on a CRF for an Unscheduled Visit, if necessary.

# 8.9.1 PARACENTESIS

If a pressure rise is observed, a paracentesis may be performed, as necessary. If a paracentesis is performed and there is no protocol-defined adverse event, the paracentesis will be documented in the subject's medical record, the applicable visit CRF and the Ocular Procedures log. If, however, the paracentesis is performed in conjunction with an AE, then the AE is recorded as such, and the paracentesis is also recorded on the AE CRF as a treatment for the protocol-defined AE (as well as the other CRFs mentioned above).

## 8.9.2 SECONDARY IOP-LOWERING INTERVENTIONS TO CONTROL IOP

If the subject requires another glaucoma procedure to control their IOP after enrollment into the study, the subject should continue to be followed according to standard of care until the adverse event resolves or 1-month post-re-intervention, whichever is longer. Following this, the subject should be withdrawn from the study.

If such secondary surgical intervention had happened more than 1 month before enrollment into the study, the subject should be enrolled, examined as per 6-month or 12-month visit schedule depending on the date of enrollment and exited from the study.

Subjects who have had a secondary IOP-lowering intervention will be considered treatment failures for the purpose of the endpoint analyses.

### 8.10 WITHDRAWAL AND DISCONTINUATION

All subjects have the right to withdraw at any point during the study without prejudice. The Investigator can discontinue any subject at any time at his/her discretion, or if continued participation in the study would result in harm to the subject. All efforts should be made by the Investigator to retain the subject in the study. If a subject withdraws prematurely from the study, a genuine effort must be made to determine the reason(s) the subject discontinued the study. The reason must be recorded in the subject's file and on the Study Exit Case Report Form. A subject may withdraw from the study on his/her own, can be withdrawn by the study investigator for reason's including but not limited to non-compliance, being unresponsive or no longer qualifies under the protocol, or withdrawn by the Sponsor for reasons including but not limited to, early closure or discontinuation of the study. For every subject that withdraws/is withdrawn from the study prior to completing the study, the study investigator should bring the subject back for a final study visit if possible unless, the subject has had a recent visit and in the Investigator's discretion, does not need a final visit. If a subject cannot be returned for a final study visit, the reason should be documented in the subject's study record.

## 8.11 SUBJECTS LOST TO FOLLOW-UP

Subjects who do not show up for a follow-up must be contacted to attempt to have them come for the follow-up. For those subjects who cannot be reached, every attempt to contact with the subject should be documented. If a subject misses two consecutive follow-up visits without any contact with the study staff, the subject will be considered lost-to-follow-up unless there is a further communication by the subject.

# 9 ADVERSE EVENTS (AES)

Adverse Events are defined below. Adverse events that occur in the eye during the trial, must be documented in the subject's records. Date of the event, its severity, treatment (if any) and the assessed relationship of the event to the study device will be recorded on the Adverse Event Case Report Form. Conditions which exist at the time the subject is enrolled will be considered pre-existing conditions and will not be recorded as adverse events unless they increase in severity during the study. Sites should document any known existing medical and ophthalmic conditions at the time of eligibility determination.

Adverse events that occurred intra, and post-operatively up to enrollment into the study will also be collected.

Adverse Event (AE)	Any untoward medical occurrence in a subject who has been treated with the device that does not necessarily have causal relationship with the treatment.
Adverse Device Effect	Any unfavorable and unintended sign (including an abnormal laboratory finding), symptom, or disease that is possibly related to the study device.
Serious Adverse Event	
 
Any untoward medical occurrence that:
 
Results in death
 
Is life-threatening
 
Requires in-patient hospitalization or prolongs existing hospitalization
 
Necessitates medical or surgical intervention to preclude permanent impairment of a body function or permanent damage to a body structure
 
Sight-threatening
 

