## **1 PROTOCOL SYNOPSIS**

Protocol Title	An Observational Multicenter Clinical Study to Assess the Safety and Effectiveness of the OMNI ® Surgical System in Pseudophakic Eyes with Primary Open Angle Glaucoma	
Investigational Device	OMNI ® Surgical System	
Study Objective		
Study Design	This is a multicenter, observational research study with no planned surgical interventions. Both prospective and retrospective data on participating subjects will be collected in the study.	
Primary Safety Endpoint	1. Rate of occurrence of sight-threatening adverse events (AEs)	
Secondary Safety Endpoints	
 
Rate of ocular AEs
 
Reduction in best corrected distance visual acuity (BCVA) from baseline
 
Secondary Surgical Interventions, including laser, for IOP control
 
	
Effectiveness Endpoints		

Rev C

Number of Subjects Enrolled and Treated	Up to 100 subjects. Up to 50 subjects who received OMNI intervention post medication washout and up to 50 subjects who received OMNI intervention without medication washout will be enrolled
Number of Sites	Up to 15 study sites in United States.
Schedule of Visits	
 
The following visits will be captured retrospectively: 
 
Subjects with preoperative medication washout: Pre-washout, Post-washout, Surgical
 
Subjects without a medication washout: Preoperative, Surgical
 
 
 
The following visits will be captured prospectively: 
 
Months 6*, 12*, 18 and 24.
 
 
 
Subjects with a preoperative washout will also undergo washout for the 12-and 24- month visits if they are on ocular hypotensive medication at these visits and return for an exam following appropriate washout period.
 
* The 6- and 12-month data can be retrospective or prospective depending on date of enrollment.
 

Interim analysis	100% subjects reaching 12 Month visit

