#### 6 STUDY ENDPOINTS

#### 6.1 PRIMARY SAFETY ENDPOINT

Rate of occurrence of sight-threatening adverse events (AEs)

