## 8.5 ELIGIBILITY AND STUDY ENTRY

Subjects will be recruited from the Investigators' patient records. Eligible subjects will consist of those patients meeting all inclusion criteria and none of the exclusion criteria, and for whom the date of surgery using the OMNI Surgical System is at least 150 days prior to enrollment in the study.

- All potential subjects should be screened for enrollment, and all eligible cases will be included up to the enrollment limit for each site.
- For the subjects who received OMNI intervention after medication washout, the eye that received OMNI surgery post medication washout should be enrolled.
- For the subjects who received OMNI intervention without medication washout if both eyes qualify, the eye with higher pre-operative medicated IOP should be enrolled. If both eyes have same pre-operative medicated IOP, right eye should be enrolled.

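### Section 9 gives conflicting rules for post-operative events still ongoing at enrolment, so the primary sight-threatening AE rate can be understated

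*Combined protocol and SAP*

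**What the plan says.** The primary safety endpoint is the rate of sight-threatening adverse events (Section 6.1). The rate of ocular adverse events is a secondary safety endpoint (Section 6.1.1).

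Subjects are found in the investigators' records and enrolled only after surgery. Section 8.5 requires that "the date of surgery using the OMNI Surgical System is at least 150 days prior to enrollment in the study". The gap can be much longer than 150 days, because the Synopsis adds: "The 6- and 12-month data can be retrospective or prospective depending on date of enrollment".

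Three statements in Section 9 govern what is recorded:

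- "Conditions which exist at the time the subject is enrolled will be considered pre-existing conditions and will not be recorded as adverse events". The only exception is an increase in severity during the study.
- "Sites should document any known existing medical and ophthalmic conditions at the time of eligibility determination".
- In the following paragraph: "Adverse events that occurred intra, and post-operatively up to enrollment into the study will also be collected".

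Other sections bear on the same question. Section 8.6 says: "Medical records will be reviewed for demographic and medical history information, preoperative, medication use data, and adverse events". Section 10.5.1 classes adverse events by their timing relative to treatment, not to enrolment. Section 9.1 makes any sight-threatening event reportable.

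**The concern.** In a study that enrols before treatment, a condition present at enrolment is also one that preceded treatment, and leaving it out of the AE count is standard. Here enrolment follows treatment by five months or more. The same wording therefore reaches conditions that arose after the operation and may have been caused by it.

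If sites apply that wording, the loss is selective. A post-operative event that resolved before enrolment is counted, but one that persisted without worsening is not. For a sight-threatening endpoint, persistent events are the ones a reader most wants to see.

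Two further problems follow. Sites may read the section differently, so their rates would not be comparable. The count would also depend on when a subject happened to be enrolled. The BCVA and slit-lamp summaries (Sections 10.5.2 and 10.5.3) would show some of the affected eyes, but they do not feed the AE rates.

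**Working it through.** The plan states no figure to reproduce. The check is a reading of the text, followed by an illustration of size.

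**Step 1. Apply both rules to each kind of event with onset between surgery and enrolment.**

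| Status at enrolment | Pre-existing rule | Collection sentence | Result |
|---|---|---|---|
| Resolved | Does not apply | Collect | Counted |
| Ongoing, later worsens | Exception applies | Collect | Counted |
| Ongoing, does not worsen | Do not record as AE | Collect | Conflict |

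The conflict is confined to the third row. The available text neither ranks the two rules nor limits pre-existing conditions to those present before surgery. The instruction to document existing ophthalmic conditions at eligibility gives such an event a second place to be entered, as history.

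**Step 2. Dependence on enrolment date.** Take a stable event with onset at month 8. In a subject enrolled at month 6 it starts after enrolment and is an AE. In a subject enrolled after month 12 the first rule makes it pre-existing. The eye and the event are the same, but the count differs.

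**Step 3. Length of the exposed period.** With 24 months taken as 730 days, the pre-enrolment period is at least 150/730 = 20.5% of follow-up, and it contains surgery and the early post-operative phase. For a subject enrolled after month 12 it is at least 365/730 = 50%. These are shares of time, not estimates of bias.

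**Step 4. Effect of one omitted event.** The inputs are up to 50 subjects per washout stratum and up to 100 in all (Section 8.3). Intervals are exact (Clopper-Pearson) 95%.

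| Eyes | Event recorded | Event omitted |
|---|---|---|
| 50 | 1/50 = 2.0% (0.05 to 10.65%) | 0/50 = 0% (0 to 7.11%) |
| 100 | 1/100 = 1.0% (0.03 to 5.45%) | 0/100 = 0% (0 to 3.62%) |

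**Step 5. Expected effect under assumed rates.** The documents give neither the event rate nor the share of events that persist, so both are assumed. Let p be the true proportion of eyes with an event, and f the share of those events that are stable and ongoing at enrolment. If every site applies the first rule, the recorded rate is q = p(1 − f), and the chance of reporting no event in a stratum of 50 is (1 − q)^50.

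| p | f | q | P(0 of 50) |
|---|---|---|---|
| 4% | 0 | 4.0% | 13.0% |
| 4% | 25% | 3.0% | 21.8% |
| 4% | 50% | 2.0% | 36.4% |
| 2% | 0 | 2.0% | 36.4% |
| 2% | 25% | 1.5% | 47.0% |
| 2% | 50% | 1.0% | 60.5% |

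The chance that at least one event is dropped is 1 − (1 − pf)^n. For p = 2% and f = 50% this is 1 − 0.99^50 = 39.5% with 50 eyes and 1 − 0.99^100 = 63.4% with 100. Since q never exceeds p, the error can only be downward.

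**The case against.** The best defence is that Section 9, read in order, makes sense. Its first paragraph opens with events during the trial, so the pre-existing sentence may do no more than stop an old condition from being logged as a new prospective event. The collection sentence comes later, is specific to the period in question and is additive. It turns on when the event occurred, not on whether it resolved. The rest of the plan agrees: charts are reviewed for adverse events (8.6), safety uses all available data (10.5), AE classes are anchored to treatment (10.5.1), and secondary interventions before enrolment count as failures (8.9.2). Sight-threatening events have further protection, because Section 9.1 makes them reportable and Section 9.3 requires prompt reporting of ocular SAEs.

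Much of this stands. Collection is probably what the sponsor intends, and the ambiguity is likely to affect non-serious ocular events more than sight-threatening ones. But none of these sections addresses an event already ongoing at enrolment, and none lifts an explicit bar on recording. A site that has classed a condition as pre-existing can reasonably conclude that it is no longer an adverse event to be collected. The analysis classes can only summarise what sites have entered.

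Two other points are fair. The visit schedules and the list of anticipated events (Sections 8.1, 8.2 and 9.2) are not in the public text, so a resolving rule there cannot be excluded. The safety analysis is descriptive, and no test or performance goal is visible that one event would overturn. The cost is an understated rate, not a wrong decision at a threshold.

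**Conclusion.** The concern holds and should be fixed. Two adjacent sentences of Section 9 give opposite instructions for a post-operative event that is ongoing and stable at enrolment, and the available text does not reconcile them.

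The size cannot be fixed from the documents. Each omitted event lowers the crude rate by 2.0 percentage points in a full stratum of 50, or 1.0 point in 100. The rates in the illustration are assumptions, and they also assume that every site applies the first rule; partial use would give a smaller bias. If all sites follow the collection sentence, or if no event is stable and ongoing at enrolment, the bias is zero. The direction is certain: any error makes the device look safer.

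**What to change.** - In Section 9, define pre-existing conditions as those present before OMNI surgery.
- State that any ocular adverse event with onset at or after surgery is recorded with its onset date. It counts in the primary and secondary safety endpoints whether it has resolved or is ongoing at enrolment.
- Use the chart review already planned in Section 8.6, and assign events to the existing classes of Section 10.5.1.
- For subjects already enrolled, check each ocular condition entered as existing for onset on or after the surgery date, and move it to the AE record where that applies.
- Report adverse events split by onset before and after enrolment, so that readers can tell chart-derived events from those observed prospectively.

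The cost is a short wording change, minor CRF guidance and a one-time check of existing-condition entries. The reported AE rate may become slightly less favourable. If the sponsor already intends these events to be collected, the change only makes that explicit.

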## 9.1 DEFINITIONS OF AE, SAE, ADE, SADE, UADE, USADE

<sup>15 All of these definitions are in conformance with the requirements 21 C.F.R. Part 803.

Unanticipated	Any serious adverse effect on health or safety, any life-
Adverse Device	threatening problem or death caused by, or associated with a
Effect	device if that effect, problem, or death was not previously
	identified in nature, severity, or degree of incidence in the
	clinical investigational plan; or any other unanticipated serious
	problem associated with a device that relates to the rights,
	safety, or welfare of subjects (21 CFR 812.3(s)). Any sight-
	threatening event, whether listed in the protocol or not, is
	considered to be reportable as a USADE.

Adverse events may be anticipated or unanticipated. All events will be assessed for seriousness, and relationship to the study device. Anticipated adverse events that are related to the study devices are ADEs (Adverse Device Effects) and when serious SADEs (Serious Adverse Device Effects). Unanticipated adverse events which are related to the study device are UADEs (Unanticipated Adverse Device Effects) and when serious SUADEs (Serious Unanticipated Adverse Device Effects).

Sight Sciences

## 9.3 REPORTING ADVERSE EVENTS AND UNANTICIPATED ADVERSE DEVICE EFFECTS

Identification, collection and reporting of adverse event information is the responsibility of the Principal Investigator. The Investigator records the date of the event, its severity,

treatment (if any) and the assessed relationship of the event to the study device on the Adverse Event Case Report Form (AE CRF).

[figure not shown]
Any ocular **serious adverse event** (SAE) should be reported to the study sponsor within one business day of learning of the event. Non-ocular SAEs should be reported to the study sponsor within two working days of learning of the event. Enter data in EDC system within two working days of learning of the event.

Any **unanticipated adverse device effects (UADE)** must be reported to the following two entities:

- 1. The study sponsor Within one working day of the investigator first learning of the event enter data in EDC; and
- 2. The reviewing IRB As soon as possible, but no later than 10 working days after the investigator first learns of the event, report per the IRB's instructions.

The sponsor will conduct an evaluation of unanticipated adverse device effects. If the sponsor determines that an unanticipated adverse device effect presents an unreasonable risk to subjects, parts of the investigation presenting risks will be terminated. Termination will occur no later than 5 working days after the sponsor makes such a determination and no later than 15 working days after the sponsor first received notice of the effect.

